Smoking status is assessed using the timeline follow-back method (Brown et al., 1998) as done previously (Lerman et al., 2004; [name] et al., 2010b) and by using breath CO to verify self-report. Participants are considered abstinent if they self-report abstinence (not even a puff of a cigarette) for >7 days prior to the Week 24 and 52 assessment and have a breath CO of <10ppm at the time-point (SRNT, 2002; Hughes et al., 2003). As per convention, participants are assumed to be smoking if they self-report to be smoking at the time-point, cannot be reached to provide data at the time-point, fail to provide a breath sample at the time-point, or provide a breath sample at the time-point that is >10ppm (SRNT, 2002).

Cessation/Smoking Rate: Daily smoking (presence and rate) will be assessed at each visit after Intake Session with the well validated timeline followback method (TLFB). These data can be used to assess

the timing and rates of lapses (smoking episodes not lasting 7 days), recovery events (return to abstinence), and relapse events, as well as to monitor changes in smoking rates (i.e., # cigarettes/day). These data will also be used to compute and assess secondary measures of smoking cessation (e.g., continuous and prolonged abstinence).

Carbon Monoxide (CO) Test: Carbon monoxide will be measured at each in-person visit to confirm smoking status.

Other Smoking Measures (secondary)

As per recommendations (Hughes et al., 2003), we will also assess: prolonged abstinence to Weeks 12, 24, and 52 (relapse is 7 consecutive days of self-reported smoking, after a 2-week grace period), continuous abstinence at Weeks 12, 24, and 52 (no smoking between the quit day and follow-up), time to 7-day relapse (no grace period), smoking rate, and lapse (smoking episodes < 7 days) and recovery (return to 24-hour abstinence) events.

Quality of Life (QOL)

The Short-Form Health Survey (SF-12) will assess QOL (Ware et al., 1996). This scale yields physical and mental subscales, has been used to assess cancer patient QOL (McCorkle et al., 2009), has demonstrated validity and reliability (Gandek et al., 1998), and has been used in smoking cessation trials with cancer patients ([name] et al., 2010a). The SF-12 will be administered at all visits following the Intake Session.

2. Statistical Analysis

Power

Power is provided for the primary aims since the exploratory aim is hypothesis generating. All comparisons are 2-sided.

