Aim 3: The analyses will assess changes in affect and cognitive impairment as mediators of treatment arm effects at Week 24 and 52. These measures are continuous difference scores. Our sample of 374 is well above the minimum sample of 200 recommended for models of this size (Haduk, 1987; Boosma & Gabrielli, 1985). The mediation hypothesis will examine the proportion of treatment effect explained (Lin et al., 1997; Vittinghoff et al., 2009), and test with a z-score generated using the delta method. Our sample of 374 gives us 80% power to observe small effects in a 1-sample test ($\delta=0.20$) when testing at $\alpha=0.05$. There are two proposed mediating pathways between treatment and outcome, so our type-1 error will be corrected to 0.025. Our sample of 374 gives us 80% power to detect small to medium effects ($\delta=0.22$) for changes in the proposed mediators.

[figure not shown]
Data Analysis

[name] will oversee analyses. Preliminary analyses will assess sample characteristics by treatment with chi-square or logistic regression (e.g., gender, dependence, depression, disease site). These variables will also be examined for their relationship to completion of outcome assessments. Variables related to treatment arm and completion of follow-ups will be included as covariates in analyses of study aims. Compliance measures will be evaluated across treatment arms, and controlled for in primary analyses. Although we will use an intent-to-treat analysis as the primary method for evaluating study aims, we will conduct a completers only analysis of study aims and examine study aims with participants lost to follow-up due to death excluded as done previously ([name] et al., 2003).

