Aim 3: Assess changes in affect and cognitive impairment and cue-elicited urges as mediators of extended varenicline therapy's effect on quit rates. The effects of treatment arm on mediators will be assessed using linear regression. Structural equation modeling will be used to obtain a more comprehensive understanding of these mechanisms. It is hypothesized that treatment arm will yield significant differences in proposed mediators and that differences in mediators will predict week 24 and 52 outcomes. We will focus on changes in mediators from baseline to week 14, when the standard therapy participants transition to placebo and the extended therapy group stay on active treatment. After first demonstrating that treatment arm affects quit rates (Aim 1), these effects will be partitioned into mediated and unmediated effects, via path and structural equation models. For example, paths *d* and *b* represent the mediated effects of treatment arm on quit rates through changes in negative affect, and path *a* represents residual effect of treatment arm on quit rates not mediated by negative affect. Path *f* represents the hypothesis that the impact of treatment arm on quit rates will depend on negative affect. Specific hypotheses will be tested by using chi-square difference tests that contrast the overall fit of this full model with more parsimonious nested models in which specific predictive effects are fixed to zero (e.g., the unmediated path *a*). Model goodness-of-fit indices will be contrasted to guide interpretation of results and determine the practical significance of statistically significant differences. Modification indices will be examined to guide model interpretation and modification. Models will be tested through Mplus, which easily accommodates the combination of binary and continuous variables. This approach allows us, in principle, to test whether treatment effects on quitting are due to specific mechanisms (e.g., reduction in negative affect). Tests for mediation by positive affect, withdrawal, cognitive impairment, and cue-elicited urges will be conducted in this fashion.

Path Model of Treatment Arm, Negative Affect, & Quit Rate

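### Aim 3 names a weak ratio test for mediation, and the path models planned alongside it name no test of the indirect effect and are not said to decide

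*Combined protocol and SAP*

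**What the plan says.** Two parts of section 2, Statistical Analysis, in the combined protocol and SAP deal with mediation.

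**Power, Aim 3.** The text reads "The mediation hypothesis will examine the proportion of treatment effect explained", cites two methods papers, and continues "and test with a z-score generated using the delta method". It gives no formula for the proportion. On error control it states "There are two proposed mediating pathways between treatment and outcome, so our type-1 error will be corrected to 0.025"; the opening of the Power section adds "All comparisons are 2-sided". Two power figures follow: "Our sample of 374 gives us 80% power to observe small effects in a 1-sample test" (effect size 0.20, alpha 0.05) and "Our sample of 374 gives us 80% power to detect small to medium effects" (0.22, for changes in the mediators). Neither is a power for the proportion explained.

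**Data Analysis, Aim 3.** Mediators are regressed on arm. Path and structural equation models are then fitted in Mplus: "After first demonstrating that treatment arm affects quit rates (Aim 1), these effects will be partitioned into mediated and unmediated effects". Paths *d* and *b* are said to carry the mediated effect and path *a* the residual effect of arm. Hypotheses are tested by comparing nested models. The one example given sets path *a*, the direct effect, to zero. No joint or product test of *d* and *b* is named, and nothing says whether these models or the z-score in the Power section settle the mediation hypothesis.

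**The concern.** The proportion explained is a ratio whose denominator is the Aim 1 treatment effect. At Week 24 that effect is planned with 80% power, so it lies fewer than three standard errors from zero. A ratio with so noisy a denominator has a wide delta-method standard error, and its z-test can miss mediation that a direct test of the two paths would find.

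There is a second problem on the log-odds scale. Adding a variable that predicts quitting enlarges the arm log-odds ratio even when arm does not affect that variable. The proportion is then pushed below zero under no mediation.

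Aim 3 carries a stated hypothesis. With two procedures of very different power and no ranking between them, the weaker one could decide the aim, or the choice could be made after both results are seen.

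**Working it through.** **The plan's own power figures.** For a one-sample test, power is Φ(δ√n − z), with √374 = 19.34.
- δ = 0.20, alpha 0.05: Φ(3.87 − 1.96) = 97.2%, not 80%.
- δ = 0.22, alpha 0.025: Φ(4.25 − 2.24) = 97.8%, not 80%.
- With n = 187 the same formula gives 78.1% and 77.9%, close to the stated 80%.
- As a comparison of two arms of 187, power is Φ(δ√(374/4) − z) = 49.0% and 45.5%. At alpha 0.025, 80% needs (2.24 + 0.84)/9.67 = 0.32 SD.

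So the stated 80% does not follow from 374 patients, and in any case does not describe the ratio test.

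**The denominator.** With 187 per arm (equal allocation is assumed):
- Week 24, 33% vs 47%: log-OR = −0.120 − (−0.708) = 0.588. SE = √[1/(187×0.47×0.53) + 1/(187×0.33×0.67)] = 0.214. Expected z = 2.75.
- Week 52, 28% vs 56%: log-OR = 0.241 + 0.944 = 1.186. SE = 0.220. Expected z = 5.4.

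The instability is therefore mainly a Week 24 problem, or a Week 52 problem if the fallback difference of 14 points applies.

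**Simulation model.** Mediator M = d·T + N(0,1), where T is arm. Logit P(quit) = b0 + a·T + b·M, with b0 and a set so that the marginal quit rates equal those in the Power section for Aim 1. The path figure is not shown, so *d* is taken as arm to mediator and *b* as mediator to quitting.
- Ratio test: proportion = 1 − (adjusted arm log-OR)/(unadjusted arm log-OR), divided by its delta-method SE with the joint sandwich covariance of the two fits.
- Two-path test: *d* and *b* both significant.
- Runs of 2,000 to 4,000 trials per scenario, two-sided.

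The quit rates, n and alpha come from the document. The path sizes are assumptions: the plan gives no mediator-to-quit effect and no expected proportion mediated.

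| Quit rates | d (SD) | OR per SD | alpha | Ratio z | Both paths |
|---|---|---|---|---|---|
| Week 24, 33/47 | 0.32 | 1.82 | 0.025 | about 9% | about 80% |
| Week 24, 33/47 | 0.32 | 1.82 | 0.05 | about 23% | about 87% |
| Week 24, 33/47 | 0.45 | 1.82 | 0.025 | 28% | 99% |
| Week 24, 33/47 | 0.22 | 1.82 | 0.025 | about 1.5% | about 45% |
| Week 52, 28/56 | 0.32 | 1.65 (log-OR 0.5) | 0.025 | about 20% | about 79% |
| Week 52, 28/56 | 0.45 | 1.82 | 0.025 | 61% | 98% |
| Week 52, 28/42 | 0.32 | 1.65 | 0.025 | 8% | 79% |

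In the first row the median 95% interval for the proportion is about 0.55 wide. With log-OR 0.5 instead, the true proportion is only 0.215.

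**No mediation (Week 24).** With d = 0 the median proportion is about −8% at OR 1.82 and about −20% at OR 2.7 per SD. In the two null cases run at nominal 2.5% (d = 0 with log-OR 0.5; d = 0.35 with no effect of the mediator on quitting), the ratio z rejects in at most 0.1% of trials and the two-path test in 2.0% to 2.6%. The two-path test does not gain its power by inflating false positives.

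**The case against.** **The path tests are already planned.** The Data Analysis section has the arm-to-mediator regression, the hypothesis that mediator changes predict quitting, and nested model tests. The ratio appears only under Power, and nothing ranks it higher. This stands in part. A reader might infer that Aim 3 would almost always report no mediation; the documents do not support that, because the path models could find it. What remains is that no test of *d* and *b* together is named, the only worked example tests the direct effect, and the only statistic attached by name to the mediation hypothesis is the z-score on the ratio.

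**The form of the statistic is inferred.** The plan does not define the proportion, and its wording does not strictly fix what the z-score is computed on. In the d = 0.32, OR 1.82, Week 24 scenario, a z on the difference in log-odds ratios has about 50% power and a delta-method z on the product of paths about 70%. A product form of the ratio has 17% to 29% where the two-path test is near 80%. This stands: the low figures and the negative offset belong to the log-odds-ratio form. All these alternatives are still weaker than the two-path test.

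**The sizes depend on chosen inputs.** This also stands. At d = 0.32 the arm-to-mediator comparison itself has 80% power at alpha 0.025, so the 80% in the first row is close to built in. A reader might infer that the ratio test has under 10% power throughout; the Week 52 rows, the alpha 0.05 row and the d = 0.45 row show otherwise. A reader might also infer that a path test would reliably detect mediation; with the plan's 0.22 read as a between-arm difference, it has only about 45%.

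**Conclusion.** The point holds as a defect in how the deciding test for Aim 3 is specified. The Power section attaches the mediation hypothesis to a z-test on a ratio, the Data Analysis section plans path models without an indirect-effect test, and the two are not reconciled.

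Read as 1 minus adjusted over unadjusted log-odds ratio, the ratio test had lower power than the two-path test in every scenario run. The gap runs from about 9% against 80% (Week 24, 0.32 SD, OR 1.82 per SD, alpha 0.025) to 61% against 98% (expected Week 52 rates, 0.45 SD). In that form the estimate is also biased below zero under no mediation.

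The direction is well supported. The sizes are illustrative and rest on equal allocation, a normally distributed mediator, complete data on 374 patients, and path effects that the plan does not give. With 262 patients (70% of 374, the expected follow-up completion), Week 24, d = 0.32 and log-OR 0.5, power is 1.5% against 60%. Aim 1 and the safety comparison are unaffected.

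**What to change.** 1. In the Aim 3 Power paragraph, replace the z-test on the ratio with the indirect effect as the deciding test: either the product of the arm-to-mediator and mediator-to-quit paths with a bootstrap confidence interval, or both paths significant at 0.025. Choose one in advance.
2. In the Aim 3 Data Analysis paragraph, state that the path models supply this test and that the nested comparison fixing path *a* addresses the direct effect only.
3. Keep the proportion of effect explained as a descriptive estimate, define its formula, and give a bootstrap or Fieller interval.
4. State power for the chosen test, with the assumed size of each path and the quit rates, and label it as conditional on those assumptions.

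The cost is wording in two paragraphs and minor programming in the software already named. No data, visits or participants are added.

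### The Aim 3 claim of 80% power for delta 0.22 does not reproduce for the planned arm-on-mediator test (0.32 SD unadjusted); alpha 0.025 covers two pathways while at least seven mediators are named, and one is not scheduled at Week 14

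*Combined protocol and SAP*

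**What the plan says.** The Power paragraph for Aim 3 describes the mediators as continuous difference scores. It plans to test mediation through the proportion of treatment effect explained, with a delta-method z-score. It then makes three statements in sequence:

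- "Our sample of 374 gives us 80% power to observe small effects in a 1-sample test", with delta 0.20 at alpha 0.05.
- Alpha is then reduced: "There are two proposed mediating pathways between treatment and outcome, so our type-1 error will be corrected to 0.025".
- Under that reduced alpha it claims: "Our sample of 374 gives us 80% power to detect small to medium effects", with delta 0.22, this time for mediator changes. No test or unit is named for this figure.

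The opening of the Power section adds "All comparisons are 2-sided".

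The Data Analysis text for Aim 3 gives the arm-on-mediator test: "The effects of treatment arm on mediators will be assessed using linear regression". Its timing is "We will focus on changes in mediators from baseline to week 14". Its heading reads "Assess changes in affect and cognitive impairment and cue-elicited urges as mediators", whereas Aim 3 under Objectives names only affect and cognitive impairment. After a worked example on negative affect, the section ends: "Tests for mediation by positive affect, withdrawal, cognitive impairment, and cue-elicited urges will be conducted in this fashion". Under Mediating Variables, the paragraph on mood also makes the anxiety and depression scales mediators. The Mediators block of Table 2 further lists smoking urges (QSU-B), the Cigarette Evaluation Scale and the Pearlin Mastery Scale.

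**The concern.** The 0.22 statement concerns mediator changes, and those changes are to be compared between arms. A two-arm comparison needs a larger standardized difference than a one-sample test on the same total, yet 0.22 is only slightly above the one-sample 0.20 printed just before it. If the figure is wrong for the planned test, a null arm-on-mediator result could be reported as well powered for a small-to-medium effect when it was not.

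Two related gaps sit beside it. An alpha corrected for two pathways does not protect a longer list of mediators, so one nominally positive mediator could be reported without the intended error control. And a mediator that is not measured at Week 14 cannot enter an analysis of change to Week 14.

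**Working it through.** **Inputs.** Total 374, power 80%, alpha 0.05 then 0.025 (Power, Aim 3); two-sided (opening of Power); regression of mediator change on arm (Data Analysis, Aim 3); under 20% withdrawal and about 70% follow-up (Accrual; neither is specific to Week 14). The allocation ratio is not stated, since the printed 187 is per site. I assume 1:1, or 187 per arm, which is the most favourable split. Normal quantiles: 1.960 (alpha 0.05), 2.241 (alpha 0.025), 0.842 (80% power).

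**1. The plan's figures as one-sample tests.** Detectable delta = (z + 0.842)/√n.

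- n = 374, alpha 0.05: 2.802/19.34 = 0.145 (plan: 0.20).
- n = 374, alpha 0.025: 3.083/19.34 = 0.159 (plan: 0.22).
- Solving for n: (2.802/0.20)² = 196.2 and (3.083/0.22)² = 196.4.

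The two printed deltas agree with each other at about 196 patients, but not at 374.

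**2. The planned two-arm test, unadjusted, in SDs of the change score.** Detectable difference = (2.241 + 0.842) × √(2/n per arm). Power at 0.22 = Φ(0.22/√(2/n) − 2.241).

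| Per arm | Basis | Detectable difference | Power at 0.22 |
|---|---|---|---|
| 187 | all 374 | 0.319 SD | 45.5% |
| 150 | 80% of 374 = 299 | 0.356 SD | 36.8% |
| 131 | 70% of 374 = 262 | 0.381 SD | 32.2% |

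A t-based check with 187 per arm gives 0.320 SD and 45.2%. A 2:1 split would give 0.338 SD. For 80% power at 0.22, n per arm = 2 × (3.083/0.22)² = 392.8, or 393.

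**3. What would bring 0.319 down to 0.22.** The ratio is 0.22/0.319 = 0.690, and its square is 0.476.

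- Covariates on the change score: R² = 1 − 0.476 = 0.52.
- Baseline adjustment at an assumed pre-post correlation of 0.5 removes 25% of the change-score variance: 0.319 × √0.75 = 0.276 SD, with power at 0.22 of about 58%.
- If delta is in SDs of the raw score, the correlation needed is 1 − 0.476/2 = 0.76 (change score) or √(1 − 0.476) = 0.72 (baseline-adjusted).

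The plan states no R², no correlation and no baseline adjustment for this test.

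**4. Mediators against alpha.** Data Analysis names five: negative affect, positive affect, withdrawal, cognitive impairment and cue-elicited urges. Anxiety and depression make seven, before the further Table 2 entries. For independent arm-on-mediator tests at 0.025 each, familywise error = 1 − 0.975^k: 4.9% for two, 11.9% for five, 16.2% for seven.

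**5. Schedule.** Mid-treatment Assessments limits the choice task to in-person visits. Table 2 makes Week 14 a phone visit and schedules the task at Weeks 0, 1, 4, 12, 24 and 52. Under Dosing, both arms receive the same treatment to Day 84 and diverge on Day 85. Week 24 is therefore the first scheduled task visit after the arms diverge, and it is also an outcome visit. The PANAS, the FACT cognitive measure, the withdrawal form and the HADS are all scheduled at Week 14.

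**The case against.** The best defence is that 0.22 is under-described rather than impossible. The test is a regression, and the Data Analysis section allows covariates in analyses of the study aims, so 0.32 SD is the unadjusted value and not a best case. A reader might infer that no calculation with 374 patients can give 0.22. That goes too far, because step 3 shows what would produce it. What remains is that the plan states none of those conditions, and the correlation or R² required is substantial.

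It can also be said that the power statements belong to the delta-method mediation test. That is plausible for the 0.20 sentence. But the 0.22 sentence is about mediator changes, and as a one-sample figure it still does not match 374.

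On multiplicity, Objectives and the Power paragraph both name affect and cognitive impairment, which fits two pathways, and the other mediators may be meant as exploratory. The plan does not say so, and the Aim 3 analysis heading sets cue-elicited urges beside those two. The path figure is not reproduced in the text available, so it cannot settle the matter.

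On timing, focusing on Week 14 does not exclude other visits, and the choice task has a separate purpose in comparing acute with chronic administration. The gap therefore concerns this one mediator, which lies outside the Aim 3 hypothesis.

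**Conclusion.** The point holds. The stated 80% power for 0.22 is not a property of the planned arm-on-mediator regression as described. Unadjusted, two-sided at 0.025 and with 187 per arm assumed, the detectable difference is 0.32 SD of mediator change, and power at 0.22 is about 45%. With 80% to 70% of patients having data, the detectable difference is about 0.36 to 0.38 SD. The two-pathway alpha does not match a list of at least seven mediators, and cue-elicited urges cannot be analysed as change from baseline to Week 14.

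Three stronger readings are not supported:

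- A reader might infer that 0.20 and 0.22 were computed on one arm. One arm of 187 gives 0.205 and 0.225, a poorer fit than about 196 to 200 patients. The cited minimum sample of 200 is another candidate, but the documents do not give the origin.
- The 12% to 16% familywise figures might be taken as the false-positive rate of a mediation claim. They apply only to the arm-on-mediator tests, if independent. A mediation claim also needs the mediator-to-quit path and follows a demonstrated Aim 1 effect. Neither its error rate nor the power of the delta-method test is derived here.
- Nothing here bears on Aim 1 or on the choice of 374 patients.

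**What to change.** - **Power.** Replace the 0.22 statement with: assuming 1:1 allocation, 187 per arm give 80% power for an unadjusted between-arm difference of 0.32 SD in mediator change at two-sided alpha 0.025, or about 0.36 to 0.38 SD if 80% to 70% of patients have data. State the test, the unit and any baseline adjustment, with the assumed correlation if one is used. Say that this is not the power of the delta-method mediation test.
- **Confirmatory mediators.** Before unblinding, name one affect score (for example PANAS negative affect, the plan's worked example) and cognitive function as the two confirmatory mediators at 0.025 each. Both are scheduled at Week 14. Label all others exploratory. If Holm is preferred, fix the full list first; with seven mediators the smallest p-value is tested at 0.05/7 = 0.0071, where the unadjusted detectable difference is 0.37 SD, and a longer list raises it further.
- **Consistency.** Reconcile the Aim 3 heading under Data Analysis with the two pathways in the Power paragraph.
- **Cue-elicited urges.** Label the analysis exploratory and name the visit. One option is Week 24 as a mediator of the Week 52 outcome, since at Week 24 task and outcome are measured at the same visit.

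The cost is wording and restated figures, with no added patients or visits. The downside is a less favourable stated detectable effect and fewer mediators that can be called confirmatory. Under the Week 24 option, cue-elicited urges also lose the Week 24 outcome as a mediation target.
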